SCHARP-FHCRC [name] Seattle, WA 98109-1024 USA

[contact] [contact]

Email: [contact]

[name] SDMC Project Manager

SCHARP-FHCRC

[name] [name]

Seattle, WA 98109-1024 USA

[contact] [contact]

Email: [contact]

MTN CORE FHI 360

[name], IBCLC Clinical Research Manager FHI 360

[name]

Research Triangle Park, NC 27709 USA

[contact], [name]

[contact]

Email: [contact]

HIV Prevention Agent Pregnancy Exposure Registry: EMBRACE Study

INVESTIGATOR SIGNATURE FORM

Version 2.0 11 February 2014

A Study of the Microbicide Trials Network (MTN)

Sponsored by:

Division of AIDS, US National Institute of Allergy and Infectious Diseases
US National Institute of Child Health and Human Development
US National Institutes of Health

I, the Investigator of Record, agree to conduct this study in full accordance with the provisions of this protocol. I will comply with all requirements regarding the obligations of investigators as outlined in the Investigator of Record Agreement, which I have also signed. I agree to maintain all study documentation for a minimum of three years after the study is closed, unless otherwise specified by the Division of AIDS (DAIDS) or the Microbicide Trials Network (MTN) Coordinating and Operations Center. Publication of the results of this study will be governed by MTN policies. Any presentation, abstract, or manuscript will be submitted to the MTN Manuscript Review Committee for review prior to submission and made available to DAIDS.

I have read and understand the information in this protocol and will ensure that all associates, colleagues, and employees assisting in the conduct of the study are informed about the obligations incurred by their contribution to the study.

Name of Investigator of Record	
Signature of Investigator of Record	Date

HIV Prevention Agent Pregnancy Exposure Registry: EMBRACE Study

PROTOCOL SUMMARY

Short Title: EMBRACE (Evaluation of Maternal and Baby Outcome

Registry After Chemoprophylactic Exposure)

Protocol Co-Chairs: [name], [name], MMed

Sample Size: Approximately 550 pregnant women and approximately 400

live infants

Study Population:

 Current or recent participants who became pregnant during HIV prevention trials, or who have or had planned exposures in pregnancy safety studies, provided pregnancy outcome was less than 1 year from the date of the EMBRACE Screening/Enrollment Visit

2. The infants resulting from those pregnancies, provided infants have not yet reached their 1-year birth date.

Study Sites: As determined by the MTN Executive Committee

Study Design: Prospective observational cohort

Study Duration: Until all enrolled participants have completed study

participation, or as otherwise determined by the study

sponsor

Primary Objectives

- 1. To compare adverse pregnancy and delivery outcomes between participant mothers assigned to an active agent with those of mothers assigned to placebo/control.
- To compare the prevalence of major malformations identified in the first year of life between infants of mothers assigned to an active agent with those of infants of mothers assigned to placebo/control.

Primary Endpoints

- 1. Pregnancy and delivery outcomes:
 - delivery prior to 37 completed weeks of gestation
 - stillbirth or intrauterine fetal demise (≥ 20 weeks)
 - spontaneous abortion (< 20 weeks)
 - ectopic pregnancy
 - · intrapartum hemorrhage
 - postpartum hemorrhage
 - non-reassuring fetal status
 - chorioamnionitis
 - hypertensive disorders of pregnancy
 - gestational diabetes
 - intrauterine growth restriction
- 2. Major malformations, defined as structural abnormalities with surgical, medical, or cosmetic importance.¹

Secondary Objectives

- 1. To compare growth parameters in the first year of life between infants of mothers assigned to an active agent with those of mothers assigned to placebo/control.
- 2. To evaluate the prevalence and persistence of HIV drug resistance mutations in plasma among HIV-infected infants.

Secondary Endpoints

- 1. Weight, length, and head circumference at birth, one month, six months and 12 months.
- HIV-1 drug resistance mutations among infants who acquire HIV-1 infection

1 KEY ROLES

1.1 Protocol Identification

Protocol Title: HIV Prevention Agent Pregnancy Exposure Registry

MTN Protocol Number: MTN-016

Short Title: EMBRACE

Date: 11 February 2014

2 INTRODUCTION

2.1 HIV/AIDS Prevention

According to the United Nations Joint Programme on HIV/AIDS (UNAIDS), approximately 34 million people worldwide were living with HIV in 2011² Widespread implementation of HIV-1 prevention services, including behavioral strategies, has had only modest impact on the rate of new HIV-1 infections in most populations, thus continued efforts to identify effective preventative modalities are needed. Many different approaches are being evaluated in clinical trials including HIV treatment as prevention³, combination HIV prevention⁴, behavioral interventions⁵, vaccines⁶, chemoprophylaxis⁷ and topical microbicides in various delivery systems.⁸ Clinical trials conducted by the Microbicide Trials Network (MTN) include Phase 1 and 2 safety trials of new compounds as well as larger, Phase 2B and 3 product efficacy trials.

2.2 Background

While pregnancy is a common exclusion criterion in trials of candidate HIV prevention agents, it does occur among participants even when contraception is provided by the trial. Additionally, some trials (e.g., MTN-002, MTN-008) have been designed to evaluate the safety and pharmacokinetics of microbicide use at term and late preterm gestation. Thus, several opportunities exist to gather and analyze pregnancy

exposure data, which can inform safety profiles for candidate HIV prevention product use among reproductive age women. The need for data on exposures and infant outcomes of all candidate HIV prevention agents during pregnancy makes this registry an essential component of ongoing efforts to investigate the safety of these products. Since opening for enrollment, the MTN-016 study has collected data on exposure to drugs in pregnancy, potential confounding and/or relevant factors (such as maternal age, disease status during pregnancy, and gestational age at exposure, etc.), and pregnancy and infant outcomes. To date, the MTN-016 study has encountered no major obstacles to implementation. It is anticipated that new parent trials will open and operate under Version 2.0 of the MTN-016 protocol, e.g., excluding participants from MTN-003 (Vaginal and Oral Interventions to Control the Epidemic [VOICE]) and MTN-008.

2.3 Study Hypotheses and Rationale

2.3.1 Study Hypotheses

We hypothesize the following:

- Exposures to prevention agents during pregnancy will not be associated with an increased risk of adverse pregnancy or delivery outcomes.
- Exposures to prevention agents during pregnancy will not be associated with an increased risk of major malformations among infants exposed *in utero*.

2.3.2 Rationale

Pregnancy safety data is an essential component of the evaluation of all candidate HIV prevention agents intended for use by reproductive age women. In addition to the inevitable early pregnancy exposures that will occur, there are many other compelling reasons for continuing microbicide-specific investigations of safety in pregnancy:

- 1. Among pregnant and post-partum women, sexual activity, including sexual activity with multiple partners, is common. Therefore, women who may become pregnant and post-partum women may be suitable target populations for HIV prevention agent use.
- 2. Data suggest that pregnancy represents a time of heightened risk for the sexual acquisition of HIV.¹³
- 3. If microbicides and/or PrEP become widely available, pregnant women will likely use them with or without evidence of safety. In the absence of safety data, possible recommendations to perform a pregnancy test prior to each use would create a logistical barrier to widespread uptake.

This registry study will be unique, in that it will also capture infant outcomes, including growth, as defined by birth weight and serial measures of length, weight, head circumference, and abdominal circumference in the first year of life. Including these endpoints among the registry data will provide a richer picture of the potential impact of study product exposure on pregnancy and infant outcomes. Potential differences in infant growth patterns between those exposed and unexposed to active study agents are readily measurable and accounted for by secondary objectives in this study. Another unique feature of this protocol is its inclusion of data collected on pregnancy and infant outcomes for participants using placebo study agents. The prospective collection of these outcome data prior to the unblinding of study treatment assignment will build a natural comparison group into the study database. The impact of study product exposure during pregnancy in the presence of HIV-infection is also unknown. While this is likely to be a rare occurrence, it is prudent to measure the potential impact on the prevalence of HIV drug resistance mutations in the plasma of HIV-infected infants.

Notably, we do not include bone mineral density (BMD) and/or bone metabolism evaluations on enrolled infants for several reasons. First, we do not believe there are sufficient data to suggest that very early gestational exposures (e.g., the 1st trimester exposures likely to be a large majority in our registry) would be associated with a detectable change in infant BMD and/or bone metabolism. Secondly, we believe that requiring routine blood draws and/or technically challenging bone imaging procedures for infants would significantly deter enrollment. This registry, in its current form, is already more involved than most pregnancy exposure registries; expanding it will require greater and unwarranted investment on the part of the participants. Further, as there are very limited data among infants to support standards for BMD and/or bone metabolism evaluations via blood work or imaging studies, the data generated would be of uncertain value.

2.4 Study Agents

Currently, MTN HIV prevention trials are focusing on antiretroviral drug-based study products. Data on these agents may be found in the Background section of parent study protocols, as well as the relevant Investigator Brochures and product package inserts.

3 OBJECTIVES

3.1 Primary Objectives

1. To compare adverse pregnancy and delivery outcomes between participant mothers assigned to an active agent with those of mothers assigned to placebo/control.

2. To compare the prevalence of major malformations identified in the first year of life between infants of mothers assigned to an active agent with those of infants of mothers assigned to placebo/control.

3.2 Secondary Objectives

- 1. To compare growth parameters in the first year of life between infants of mothers assigned to an active agent with those of mothers assigned to placebo/control.
- 2. To evaluate the prevalence and persistence of HIV drug resistance mutations in plasma among HIV-infected infants.

4 STUDY DESIGN

4.1 Identification of Study Design

The HIV Prevention Agent Pregnancy Exposure Registry will be a prospective observational cohort investigation of women with exposures to active and non-active study agents in trials investigating candidate HIV prevention agents and the infants resulting from those pregnancies. Parent trial participants should be offered enrollment in the Registry whenever it is determined that there has been an exposure to a study agent during pregnancy.

Optimally, participant mothers will be enrolled in MTN-016 prospectively (prior to the outcome of pregnancy being known). Participant mothers may also be enrolled in the registry after the pregnancy outcome is known, but only up until one year following the date of pregnancy outcome. Sites are encouraged to enroll participants as early in pregnancy as possible to maximize the validity of the data. Further information on planned analyses is available in Section 10.

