5.2 Inclusion Criteria: Mother

Individuals who meet the following criteria are eligible for inclusion in the study:

- 1. Able and willing to provide written informed consent to take part in the study
- 2. During participation in a parent protocol, has/had a known confirmed pregnancy, meeting at least one of the following sets of criteria in A or B:
 - A: Two consecutive monthly study visits, at least 14 days apart, with positive pregnancy tests, in the absence of signs/symptoms of miscarriage or participant report of pregnancy termination.
 - B: One or more of the following assessments:
 - Auscultation of fetal heart tones
 - Positive pregnancy test confirmed by clinic staff in the presence of clinically confirmed enlarged uterus
 - Positive pregnancy test confirmed by clinic staff in the presence of missed menses (no menses occurring at least 60 days from the first day of the last menses) by participant report Clinical assessment of fetal movement
 - Demonstration of pregnancy by ultrasound
- 3. Able and willing to provide adequate locator information, as defined in site SOPs

Note: Participants do not have to be currently enrolled or engaged in follow-up in a parent protocol to participate in EMBRACE.

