10.7 Data Analysis

In most cases, the analyses will be stratified by parent protocol. However, when appropriate, analyses combining data from multiple protocols may be conducted. When the use of descriptive statistics to assess group or site characteristics or differences is required, the following methods will be used: for categorical variables, the number and percent in each category; for continuous variables, the mean, median, standard deviation, quartiles and range (minimum, maximum). Typically, within-arm assessment of the change from the baseline measurement to a follow-up measurement will be analyzed using McNemar's test (for categorical response variables) or the paired t-test or Wilcoxon signed-ranks test (for continuous variables). In general, when use of formal testing to assess differences between study arms is required, the following methods will be used: for binomial response variables, chi-square tests (or Fisher's exact test, if appropriate) and logistic regression; for continuous variables, t-tests and linear regression, or nonparametric methods if data are non-Normal. To assess baseline differences between study arms, participants will be compared for baseline characteristics including demographics and laboratory measurements using descriptive statistics.

The proportion of participants with adverse pregnancy and delivery outcomes (as specified in Section 10.2.1) will be compared by study arm using a Fisher exact test or chi-square test, depending on the prevalence, with a two-sided level of significance. The proportions of major malformations observed in infants will be compared using the same methods.

For each of the growth parameters (i.e., birth weight, serial length, weight, and head circumference), the mean observed in the active agent and non-active agent groups will be compared using a Student's *t*-test at selected time points: birth, one, six, and 12 months. More generally, GEE (generalized estimating equation) methods and robust variance estimates will be used to evaluate group differences over the first year. Incomplete data from infants that are lost to follow-up or terminate early in the study

(including from death) will be included in these analyses if a growth parameter is available at one of the selected time points.

Among infants who acquire HIV-1 infection, the proportion of infants with HIV-1 drug resistance mutations will be compared by study arm using Fisher's exact test with a two-sided level of significance.

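### The primary maternal comparison ignores when women enrolled, leaving it open to outcome-dependent selection and, for spontaneous abortion, to left truncation

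*Protocol*

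**What the plan says.** **Entry.** Protocol Section 4.1 prefers enrolment before the outcome but does not require it: "Participant mothers may also be enrolled in the registry after the pregnancy outcome is known", with a limit of one year after that outcome. The same section gives the reason for early entry: "Sites are encouraged to enroll participants as early in pregnancy as possible to maximize the validity of the data". It then refers the reader to Section 10 for the analyses. Under the note to Section 5.2, a woman need not still be in parent-trial follow-up. Section 4.4 keeps accrual open for as long as funding lasts.

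**Eligibility.** Section 5.2 offers two routes. Criterion A is "Two consecutive monthly study visits, at least 14 days apart, with positive pregnancy tests, in the absence of signs/symptoms of miscarriage", or a report of termination. Criterion B accepts any one of several clinical or ultrasound confirmations.

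**Endpoint.** Section 10.2.1 lists spontaneous abortion before 20 weeks among the primary endpoints.

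**Analysis.** Section 10.2 defines the women analysed only by Section 5.2. Section 10.7 then says: "The proportion of participants with adverse pregnancy and delivery outcomes (as specified in Section 10.2.1) will be compared by study arm", by a Fisher or chi-square test. Nothing in Section 10 mentions time of enrolment.

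**Rationale.** Section 2.3.2 rests the comparison on blinded, prospective data: "The prospective collection of these outcome data prior to the unblinding of study treatment assignment will build a natural comparison group".

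**The concern.** The protocol recognises that time of entry affects validity, yet its stated primary analysis does not use it. Two separate problems follow.

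- **Selection on outcome.** A woman who enrols after the outcome may be more or less likely to join because of that outcome. While the parent trial is blinded, this should be roughly alike in the two arms. Nothing closes enrolment at unblinding, so a woman, and the site recruiting her, may know both the outcome and the arm, and she would still count equally in the primary test.
- **Left truncation.** A woman who enrols while pregnant has by definition not yet lost the pregnancy. Criterion A adds a survival condition before she is even eligible. Losses before entry are therefore under-represented, and spontaneous abortion is the endpoint most affected.

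Section 2.3.1 hypothesises no increased risk. In that setting, an analysis that tends to shrink a real increase in early loss errs in the unsafe direction.

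**Working it through.** **1. The plan's own figure.** Section 10.3 claims at least 80% power for a 16-point difference, with 79 women per arm and 5% in the placebo arm. The significance level is not given, so two-sided 0.05 is assumed. Exact power of the Fisher test is 78.7% at 15 points (5% v 20%) and 83.0% at 16 points (5% v 21%). The figure reproduces and is not in dispute. It takes the observed proportions as given and says nothing about entry.

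**2. How women entered (Section 10.3, MTN-003).**
- Criterion A: 195/212 = 92.0%.
- Criterion B: 17/212 = 8.0%.
- Enrolled among those reporting a pregnancy: 212/428 = 49.5%. This is an enrolment fraction. It mixes ineligibility, unwillingness and loss to follow-up, is not split by arm, and does not measure bias.

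**3. Left truncation.** Let r be the true risk of spontaneous abortion and F the share of those losses that occur before entry. Among women who enter while still pregnant, the crude proportion is

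f = r(1 − F) / (1 − rF).

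- *Same r and same F in both arms:* the difference is 0. Only the level falls, because f < r whenever F > 0 (for 0 < r < 1).
- *Different r, same F:* the observed difference is (r1 − r0)(1 − F) / [(1 − r1F)(1 − r0F)]. For 0 < F < 1 this is smaller than r1 − r0 whenever r0 + r1 − r0r1F < 1, so always when the two risks sum to less than 1. For the plan's 5% and 21%, the sum is 0.05 + 0.21 = 0.26, so the difference shrinks. It equals the full 16 points at F = 0 and falls to 0 as F approaches 1.
- *Same r, different F:* a difference appears although there is no effect.

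The protocol gives no distribution of gestational age at entry and no timing of losses. F is therefore unknown, and the direction can be stated but not the size.

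**4. Selection among women enrolled after the outcome.** Let p be the true risk of an outcome, and let w1 and w0 be the enrolment probabilities of women with and without it. Then

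observed odds = [p / (1 − p)] × (w1 / w0).

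- If w1/w0 is the same in both arms, the levels are distorted but the odds ratio between arms is not. With no true effect, the difference stays 0.
- If w1/w0 differs by arm, the odds ratio is multiplied by the ratio of the two values of w1/w0.

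Blinding is the main reason to expect equal values of w1/w0. Section 2.3.2 relies on it, but no enrolment rule secures it.

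**5. The passages side by side.** Section 4.1 says timing matters and refers to Section 10. Section 10.2 admits every woman who meets Section 5.2. Section 10.7 names the proportion and the test. No step separates women enrolled before the outcome from those enrolled after it, or uses gestational age at entry.

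**The case against.** The best case for the plan has five parts.

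- **Early losses can enter.** Criterion B can admit a woman on one staff-confirmed positive test with missed menses, or on ultrasound alone. Section 5.2 also accepts a past confirmed pregnancy. A woman who miscarries after confirmation may therefore still enrol, and retrospective entry partly offsets the truncation. This stands. A reader might infer that early losses never enter, and the document does not support that. It also means that restricting the set to prospective enrolees, with no other change, would remove some recorded losses.
- **No arm difference in entry is shown.** Criterion A works through monthly parent-trial visits, Section 5.1 recruits as soon as possible after pregnancy is identified, and Section 10.4 leaves blinding to the parent trial. This stands too. Enrolment after unblinding is permitted, but the document does not show that it happens.
- **Other safeguards exist.** Section 4.2 assesses shared outcomes primarily in the parent protocol. Section 10.7 mostly stratifies by parent protocol, names logistic regression in general terms, and cautions about interpretation. These help only in part. All eleven maternal outcomes remain primary endpoints tested here, stratification does not separate early from late entrants within one trial, and the caution concerns who becomes pregnant, not who enrols or when.
- **A statistical analysis plan may settle this.** That is fair for endpoint denominators. A reader might want to add that delivery outcomes are divided by the wrong risk set, but that is ordinary content of a plan not shown here. It is weaker for timing, because Section 4.1 points to Section 10, and Section 10.7 already fixes the proportion and the test.
- **Some harms are easily overstated.** A reader might infer that an agent causing early loss could look neutral on spontaneous abortion and protective on preterm birth. The same losses cannot do both. Those before entry are missing from the denominator as well, and those in the denominator are counted as losses.

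**Conclusion.** The point holds as a vulnerability in the stated analysis. It is not a demonstrated bias, and a reader who concludes that the comparison is biased goes further than the document allows. If entry and selection are alike in both arms and the agent has no effect, the between-arm difference is not biased and only the absolute proportions are distorted.

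The comparison goes wrong in two situations:

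- Entry or selection differs by arm, which becomes more plausible after unblinding.
- The agent has a true early effect. The difference in spontaneous abortion is then pulled towards zero even with identical entry in both arms.

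The second result assumes two risks that sum to less than 1, as in the plan's own example, and some losses before entry. The size of either distortion cannot be derived from the protocol, which gives neither gestational age at entry nor the share enrolled after the outcome. This is an inexpensive improvement to the primary analysis and is best settled before any analysis by arm.

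**What to change.** Amend Section 10.7 in two linked steps.

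- **(a)** For the maternal outcomes, make the primary set the pregnancies enrolled before the outcome was known and before the parent trial was unblinded. Report all enrolled women, including those enrolled after the outcome, as a sensitivity analysis.
- **(b)** Together with (a), compare spontaneous abortion and pregnancy loss by time-to-event methods on the gestational-age scale, with delayed entry at gestational age at enrolment. Step (a) should not be adopted without (b), because restricting to prospective enrolees while keeping the crude proportion would leave the truncation in place and drop some losses now captured.

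**Cost.** The change is one of wording and needs no new visits. The enrolment visit is Day 0 (Section 7.1), gestational age at outcome is recorded (Section 7.4), and the one-year eligibility limit requires the outcome date, so gestational age at enrolment can be derived. The primary set shrinks by the share enrolled after the outcome or after unblinding. One limit remains: delayed entry cannot recover losses before the earliest gestational age at which any woman enrols, and the report should say so.
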